# 2. Qualitative data collection: parent survey and focus groups / semi-structured interviews

Qualitative data collection tools will include a parent / carer survey and focus groups and/or semi-structured interviews to collate opinions and experiences around the assessment and management of neonatal jaundice. Themes around the impact of neonates' natural skin tone and / or ethnicity on jaundice assessment and the acceptability of different methods of assessment will be explored and compiled.

These tools will be optional extra sections of the study which will be signposted to, both verbally and written within the parent information sheet, at the point of enrollment into the qualitative data section. Links within the PIS will take parents to a secure web-based survey platform containing an electronic consent form for this survey. Separate links will provide the additional option to sign up to parent focus groups or semi-structured interviews, with a separate electronic consent form for recording of sessions.

The survey will include multiple choice and free text guestions (See Table 2).

Focus groups will include 4-6 consenting participants and will run on approximately 2 occasions. Senior study leads will guide appropriate content for discussion and parent representative leads will help to facilitate groups.

Semi-structured interviews will run for 30-45 minutes and be recorded after consent. Senior study leads will guide appropriate content for discussion and parent representative leads will help in the inclusion of particular themes.

Themes addressed will include: Understanding of jaundice and experiences of assessment; Interactions between natural skin colour / race / ethnicity and the assessment of jaundice; Opinions on current jaundice guidelines (from local to international); Empowering parents: Parental education on jaundice, its detection and the deteriorating infant (in view of the RHO report recommendation); Opinions on changing practice.

One recommendation from the Race and Health Observatory report was the need for an urgent review and update of written materials given to parents, around detecting jaundice and a deteriorating infant. Therefore this has been included as one of our themes. In addition, a recent paper highlighted the current differences between national and international guidance on the assessment and management of neonatal jaundice. These broad principles will be introduced to parents with short relevant excerpts to generate a discussion on their opinions of different approaches (see Appendix 3 for Focus Group and Semi-Structured Interview Framework).

**Table 2: Datapoints collected for Secondary Objective 3** 

Datapoint	Source	Collection timepoint
Parent and carer survey	•	•
Eligibility confirmation	Microsoft Forms consent	Time of survey completion
Participant identifier	Microsoft Forms	Time of survey completion
Section 1: Experience of Jaundice detection and the Impa	act of Skin Tone	•
What do you understand by the term "newborn jaundice"?a	Survey	Time of survey completion
How would you rate your experience of having your baby assessed for jaundice? c	Survey	Time of survey completion
What led you to give that rating? a	Survey	Time of survey completion
Was there anything that concerned you about how your baby was tested, treated or how you were kept informed, or not? b	Survey	Time of survey completion
(If yes) Please tell us more about your answer.a	Survey	Time of survey completion
Have you had any other experiences of newborn jaundice? a	Survey	Time of survey completion
(If yes) Tell us briefly about this.a	Survey	Time of survey completion
Was there anything that concerned you about how the baby was tested, treated or how you were kept informed, or not? b	Survey	Time of survey completion
(If yes) Tell us briefly about this.a	Survey	Time of survey completion
Section 2: Perception of care and communication		·
Were you given any information or guidance by healthcare professionals on how to look for signs of jaundice in your baby? b	Survey	Time of survey completion
(If yes) What type of information or guidance did you receive? b	Survey	Time of survey completion
(If yes) Did this include an explanation of how your baby's natural skin tone might affect signs of jaundice?b	Survey	Time of survey completion
(If yes) Did this include pictures of jaundice in a baby that matched your baby's natural skin tone? b	Survey	Time of survey completion

(If yes) Do you feel confident in looking for signs of jaundice in your baby after receiving this information?	Survey	Time of survey completion
Whom would you first approach for advice if you were concerned your baby might have jaundice? b	Survey	Time of survey completion
How and when would you approach a healthcare provider to check your newborn baby for jaundice? a	Survey	Time of survey completion
Section 3: Recommendations		
What are your views on how health professionals currently identify jaundice? Are there any aspects you think could be improved? a		
What is one thing you would like healthcare professionals to understand better about identifying jaundice in babies with different skin tones? a		
Section 4: Demographic information		
Self-identified ethnicity of participant b	Survey	Time of survey completion
How many children (including this baby) have you had?b	Survey	Time of survey completion
a Freetext answer. b Multiple choice answer. c Likert scale.		

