### 6.4. Secondary endpoints

- 1. Diagnostic methods used to assess jaundice in neonates of different skin tones
- 2. Immediate management of neonates following jaundice assessment

[Assessed through data collected by local teams during prospective data collection]

3. Number of clinical practice guidelines used and variance between guidelines

[Assessed through data collected in pre-study survey of local leads at each site]

- 4. Acceptability of a validated neonatal skin tone tool in a diverse population of parents and carers
- 5. Parent and carer understanding of neonatal jaundice
- 6. Parent and carer opinions and experiences of the impact of skin tone and/or ethnicity on jaundice assessment in neonates

[Assessed through data collected in parents/carer completed surveys and through focus groups and semi-structured interviews]

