#### Informed consent for qualitative data (Secondary Objective 3):

- At the time of enrollment into quantitative data collection, the research team member will verbally explain the optional additional parent survey and parent focus group and/or semi-structured interview enrollment, giving parents the opportunity for further questions.
- The participant information sheet will include a link to the parent survey and an electronic consent form, as well as a separate link to further information on focus groups and / or semi-structured interviews and how parents can sign up to these.
- Electronic consent for the recording of focus group or semi-structured interview transcripts will be obtained at the start of the groups or interviews.
- Parents and carers can withdraw their consent to participate and for their data to be stored and used at any time. It will be made clear that their medical care will not be affected either way.

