### Survey data:

 Within the participant information sheet, a QR code and written link will be provided for parents to access and fill in the web-based survey.

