#### Study Process & Practical Considerations

- Some parents wanted clearer expectations on timing—when assessments happen, how long they take, and who conducts them.
- Suggestion to move the discussion about jaundice to the beginning of the conversation.
- Preferred approach: Inform parents how long they have to read materials and specify how much time further steps will take.
- Need for clearer explanation about what data is collected from medical records, with brief examples to avoid it feeling vague or intrusive.

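### The parent survey asks what information healthcare professionals gave about jaundice without excluding the research team's own conversation, so parents may count the study approach as routine information

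*Protocol*

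**What the plan says.** Section 6.4 lists as secondary endpoint 5 "Parent and carer understanding of neonatal jaundice". It states that endpoints 4 to 6 are "Assessed through data collected in parents/carer completed surveys and through focus groups and semi-structured interviews".

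The survey items are in Table 2 of section 8. The first is a free-text item, "What do you understand by the term" newborn jaundice. The survey's Section 2 then asks "Were you given any information or guidance by healthcare professionals on how to look for signs of jaundice in your baby". Parents who answer yes get follow-ups on the type of information, whether it covered the effect of the baby's natural skin tone on signs of jaundice, whether it had pictures matching that skin tone, and whether they now feel confident. The only collection timepoint that Table 2 gives is "Time of survey completion".

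On access, section 9 says "The participant information sheet will include a link to the parent survey and an electronic consent form", and, where it describes the survey, "Within the participant information sheet, a QR code and written link will be provided for parents to access and fill in the web-based survey". The sheet comes with a verbal explanation of the study's aims, what it involves, and its possible harms and benefits (section 9, opt-out consent). The people who give it are paediatric resident doctors belonging to the direct care team (section 8). Parent feedback on the role-play of this approach, in Appendix 2, includes "Suggestion to move the discussion about jaundice to the beginning of the conversation".

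**The concern.** The Section 2 items are naturally read as describing what routine care tells parents. Parental education is a stated theme of the qualitative work, and section 8 links it to a recommendation to review the written materials given to parents. If some parents answer yes because of the research conversation, the survey will show more information given than routine care provided. The gap that the study wants to describe will then look smaller than it is.

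The skin tone follow-up is the most exposed. The study's subject is skin tone and jaundice assessment, and the follow-up asks whether parents were told about that link.

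**Working it through.** There is no figure to reproduce. The check sets the relevant sections side by side.

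1. **Order.** The survey is signposted in the information sheet and explained verbally at enrolment (sections 8, 9 and 13.1). Parents who opt out of the quantitative part may still take part (section 7.1), but no other route to the survey is described for them. Survey answers therefore follow the approach, and there is no earlier measurement.

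2. **Content of the approach.** The study's aims are explained (section 9), and both primary objectives concern neonates of different skin tones (section 6.1). Explaining them is likely to convey that skin tone may matter for jaundice assessment. Appendix 2 confirms that the conversation includes some discussion of jaundice. It does not say what that discussion covers.

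3. **Who makes the approach.** The data collectors are doctors in the direct care team (section 8), so a parent can reasonably regard them as healthcare professionals in the sense of the item. Parents in the Appendix 2 group also asked that the study paperwork be clearly marked as research and not part of the health record. Confusion between research and care is thus a risk that the parents raised themselves.

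4. **What the items separate.** No Table 2 item excludes the research team, refers to the time before the approach, or asks where the parent's understanding came from.

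5. **What the other sources separate.** The Appendix 3 frameworks ask about past as well as present understanding, its source, and when information was given. They reach few parents: about two focus groups of 4 to 6, so 2 × 4 = 8 to 2 × 6 = 12 parents, plus interviews with a small sample. The survey is offered to about 560 (section 10.1).

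6. **Direction and size.** Let g be the proportion given guidance in routine care, and m the proportion of the remaining parents who count the research conversation as guidance. The survey then shows g + (1 − g)m, an excess of (1 − g)m. This is zero if m = 0 and positive otherwise. The documents give neither g nor m, so any percentage would only restate an assumption. For the follow-ups, an extra yes also enlarges the group who are asked. The skin tone item is likely to be pushed up; the direction for the picture and confidence items is not fixed.

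**The case against.** The strongest case on the other side has five parts.

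- **Content.** The explanation is described as being about the study. Explaining a study is not guidance on how to look for signs of jaundice, and the follow-up on type of information may show what a yes refers to.
- **Evidence.** The information sheet is not in the document, and the mention of a jaundice discussion comes from feedback on a role-play.
- **Definition.** Endpoint 5 is not defined as understanding before the study or as the product of routine care. The free text is analysed thematically, with no before-and-after comparison.
- **Other influences.** Every baby is already having a bilirubin test, so ordinary clinical conversations shape the answers too.
- **Appendix 3.** It already asks about past understanding, source and timing.

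Most of this stands. A reader might infer that endpoint 5 partly measures the study's own teaching, and that understanding is therefore overstated. The document does not support that. Nothing in it says that the team teaches what jaundice is, and asking about current understanding is a legitimate choice.

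The objection does not remove the ambiguity over attribution. The type-of-information follow-up is not described as identifying the research team, and it does not tell the parent to leave that conversation out. Appendix 3 covers too few parents to resolve it for the survey.

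**Conclusion.** The point holds as a minor wording weakness in one part of a descriptive secondary objective. The order of events and the lack of any exclusion or source item are documented. That some parents will credit the research conversation as information from healthcare professionals is plausible but not shown. It rests on two assumptions: that explaining the aims conveys something about skin tone and jaundice, and that parents do not set the research doctors apart from those giving care.

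If both hold, the proportion reporting information received is overstated by an amount that the documents do not allow one to calculate. For endpoint 5 itself, the supportable statement is narrower: its survey part records understanding after the study approach, and the report should say so.

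**What to change.** - Begin the Section 2 information item with *Apart from the research team, …*, so that it and its follow-ups refer to routine care.
- Keep the present-tense item on understanding. Replacing it with recalled earlier understanding would give up a direct measure for one that depends on memory.
- Add one short item after it on where that understanding came from, modelled on the source question in Appendix 3, with the research team as one of the options.
- Report the survey part of endpoint 5 as understanding after the study approach.
- Leave Appendix 3 unchanged.

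The cost is a few added words, one short extra item and slight recall error when parents separate the research conversation from other contacts. It is cheapest to do before the survey is translated. No new visit, clinical data or sample is needed.

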## 3. Guideline and local practice information (Secondary Objective 2)

Local leads at each participating site were invited to complete a web-based survey regarding local practices with regards to jaundice assessments in neonates. Local guidelines and information leaflets, where available, were submitted to the REACH network for further narrative analysis. Information extracted from these guidelines will focus on mentions of skin tone, use of routine jaundice screening, thresholds to perform SBRs based on TcB readings, deviation from national guidelines, and availability of community jaundice assessments and/or treatment.

#### **Data Entry Methods**

Skin tone and clinical data collected from each participant will be recorded via a Case Report Form (CRF) and stored in a secure database (REDCap). Responses from the parent survey will be collected anonymously onto the secure NHS Microsoft 365 Forms web-based platform, which has routinely been used in other studies. Parent focus group and interview data will be recorded and transcriptions will be securely stored for data extraction to create a narrative summary.

# 9. Study procedures

#### **Opt-out Consent (Primary Objectives and Secondary Objective 1):**

- An opt-out consent model will be used for the primary objectives. This means that all eligible participants will be enrolled unless either of the parents / carers actively opt out. However, agreement from one parent is sufficient if the second parent is not present.
- A verbal and written explanation of the study will be provided, explaining the study objectives, procedures, risks, and benefits alongside the opt-out consent model.
- The written information will be available in a range of languages appropriate to the local population for each site.
- If required, a professional translator will be used to translate all relevant information, either in person or telephonically.
- Parents will be given a minimum of 15 minutes to consider the information and to ask questions as required, before study data is collected. The PIS will contain details on how to contact the study team to opt-out at any later stage.
- If parents opt-out of inclusion in the study, there will be no impact on the routine care provided

#### Informed consent for qualitative data (Secondary Objective 3):

- At the time of enrollment into quantitative data collection, the research team member will verbally explain the optional additional parent survey and parent focus group and/or semi-structured interview enrollment, giving parents the opportunity for further questions.
- The participant information sheet will include a link to the parent survey and an electronic consent form, as well as a separate link to further information on focus groups and / or semi-structured interviews and how parents can sign up to these.
- Electronic consent for the recording of focus group or semi-structured interview transcripts will be obtained at the start of the groups or interviews.
- Parents and carers can withdraw their consent to participate and for their data to be stored and used at any time. It will be made clear that their medical care will not be affected either way.

## **Screening and recruitment:**

- On data collection days, staff members carrying out jaundice assessments in relevant inpatient areas will be notified and asked to alert the research team when any neonates are undergoing their first TCB or SBR
- Standard clinical care will not be delayed for enrollment
- Identification of potential eligible babies will occur via a written identification table in postnatal areas. Outcomes, i.e. included or excluded, and reasons for exclusion will be noted in the infant's clinical record.
- The research team at each site will consist of the local lead and a number of additional data collectors who have undergone training. These individuals will review whether or not these neonates meet the eligibility criteria, and approach the birthing parent to discuss the study if eligible
- Study data will be collected in participants where all eligibility criteria are met

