The updated 2023 NICE guidance on neonatal jaundice assessment and management undertook a literature search for papers relating to use of TcB in babies of different skin tones . Only two studies were identified that compared the relationship of TcB and SBR measurements in neonates of multiple skin tones and/or ethnicities. Maya-Enero et al used the Neomar skin colour scale to compare TcB-SBR correlation in neonates of four different skin tone groups . The study found increased variance with darker skin tones. However, of a sample size of 1359, only 23 babies were in the darkest skin tone group. Furthermore, this was a single site study and multiple comparison points from the same participants were included in the analysis, limiting internal and external validity. A second study conducted by Starowicz et al included 201 mostly premature neonates. They found that TcB overestimated bilirubin and was less precise in non-caucasian babies. This study is limited by sample size and the lack of defined skin tone groups - the study instead relies on the broad ethnicity categories of caucasian vs non-caucasian.

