### 5.2. Rationale

The recent NHS Race and Health Observatory review of neonatal assessment and practice in Black, Asian and minority ethnic newborns highlights the potential for bias in the assessment of jaundice in neonates with darker skin tones. While multiple factors are likely to contribute to this, the failure to effectively detect jaundice in darker skinned neonates may play a role. In clinical practice, visual assessment remains a common indication for further jaundice investigations (e.g. TcB or SBR). The relationship between neonatal skin tone and jaundice assessment and diagnosis needs to be further explored.

Our first primary objective is to assess the level of first bilirubin measurement in neonates of different skin tones. This will enable us to determine if neonates with darker skin tones are only being assessed for jaundice once they have reached a higher bilirubin level, compared to lighter skinned neonates.

The second primary objective is to evaluate the agreement between TcB and SBR measurements in neonates of different skin tones.

During protocol development, parents and carers of infants in a range of London boroughs were invited to complete a survey to explore the need for the study including an exploration of parental experiences and concerns related to jaundice assessment in the context of different ethnic and racial backgrounds. Survey results represented a wide range of self-identified ethnic backgrounds and a significant proportion felt that their baby's ethnicity impacted their jaundice assessment, with a variety of reason why this might have been. We have used the results to inform protocol development in a number of ways. For example, to formulate focus group and semi-structured interview themes. Parent representatives also agree that the rationale for our study is well founded and the answers to the questions we have posed, will be valuable in the improvement of care for babies and families of all backgrounds.

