## 6.3. Primary endpoints

- Absolute value of first bilirubin measurement in neonates of different skin tones
- 2. Value of first bilirubin measurement relative to NICE phototherapy / exchange transfusion treatment lines in neonates of different skin tones
- 3. Age of neonates of different skin tones at first bilirubin measurement
- 4. Indication for bilirubin assessment in neonates of different skin tones

[Assessed through data collected by local teams during prospective data collection]

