#### 7.1. Inclusion criteria

Participants will be recruited for the Primary Objectives (quantitative) data collection if they fulfil the following criteria:

- 1. Neonates born at ≥ 34 weeks gestation, now between 0-14 days postnatal age
- 2. Inpatients on any ward providing postnatal care excluding the neonatal unit or paediatric ward
- 3. Undergoing first objective assessment of bilirubin level for any reason (i.e. targeted screening, suspected jaundice by healthcare professional, suspected jaundice by parent / carer, poor feeding, any other clinical indication)
- 4. Age of parent/ carer ≥18 years

Participants will be recruited for Secondary Objective 3 (qualitative) data collection (survey and / or focus groups / semi-structured interviews) if they fulfil the following criteria:

- 1. Parent or carer of neonate eligible for inclusion into the quantitative data collection section of study (even if they have opted out of quantitative data collection).
- 2.  $\geq$ 18 years of age.

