Primary objective 1 will be using a linear mixed model, with skin tone and confounders as fixed effects and hospital as a random effect. The outcomes will be the coefficient difference between baseline skin tone and the other 3, with 95% CI.

Primary objective 2 will use the Bland-Altman to detect differences of measurement between skin tones, stratified by method of how the measurement for how serum bilirubin was taken. The mean of the differences will be provided with 95% CI, along with the IQR of difference with accompanying p-value. The rate of over/under-estimation will also be estimated between different skin tones. Bland-Altman plots will be reported as well as Specificity and sensitivity analyses using Receiver operating characteristic (ROC) curves.

Secondary Objective 1: Primary length of admission differences between skin tone will be compared using survival analysis of time to event data (Kaplan-Meier plot, Cox Proportional Hazards Model). The need for interventions including phototherapy and exchange transfusion will be done using generalised linear mixed models, with outcomes reported as Odds Ratios with 95% CI.

Age of infant at measurement is an important metric and shall be included as a fixed covariate in all models other than Bland-Altman (baseline model). Additionally, IMD and gestational age may be included as additional covariates (adjusted model). However, due to the complex relationship between skin colour and medical intervention, we run the risk of over-adjusting on covariates and inducing collider bias and/or mediators. For example, skin tone may affect what the indication for jaundice assessment was, and this in turn may affect the outcome of bilirubin and if there was a delay for treatment, making it a mediator. With sufficient time, this relationship may be explored to see if different skin tones are affected by how their jaundice is first indicated, which influences clinical guidelines if an association is found between skin tone and indication which in turn affects bilirubin levels.

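### Primary Objective 1 does not say which method defines the first bilirubin value, so a tone difference could partly reflect TcB error rather than assessment at a higher true level

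*Protocol*

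**What the plan says.** - **Entry.** Section 7.1 admits infants "Undergoing first objective assessment of bilirubin level for any reason". Section 9 (Screening and recruitment) has staff "asked to alert the research team when any neonates are undergoing their first TCB or SBR". Either method qualifies.
- **Outcome.** The first primary endpoint in 6.3 is "Absolute value of first bilirubin measurement in neonates of different skin tones". No method is named.
- **Interpretation.** Section 5.2 says the objective will "determine if neonates with darker skin tones are only being assessed for jaundice once they have reached a higher bilirubin level" than lighter-skinned neonates.
- **Model.** Section 10.2: "Primary objective 1 will be using a linear mixed model, with skin tone and confounders as fixed effects and hospital as a random effect". The covariates it goes on to name are age at measurement and, optionally, deprivation index and gestational age. Method is not among them. Stratification by method appears only for Primary Objective 2, and there by type of serum test.
- **A conflicting hint.** The sample size update in 10.2 uses bilirubin measures, skin tone and age at TcB measurement, which suggests a TcB outcome. Table 1 (section 8), however, records the value relative to the treatment line under SBR only.
- **Evidence on TcB.** Section 5.1 says of one cited study: "They found that TcB overestimated bilirubin and was less precise in non-caucasian babies". Of the other, which used the protocol's own skin colour scale, it reports greater variance in darker tones.
- **Data held.** Table 1 and section 13.1 have method, device, value and time recorded.

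**The concern.** Objective 1 reads a higher first value in darker infants as assessment at a higher bilirubin level. That reading needs the measurement error to be unrelated to skin tone. Primary Objective 2 exists because the protocol regards that as an open question, yet nothing in 10.2 carries its result back into Objective 1.

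If first TcB and first SBR values enter one outcome and TcB error differs by tone, the error passes into the tone coefficient. Adjusting for age and hospital does not remove it. A uniform TcB bias could also leak in if the share of infants tested first by TcB differs by tone, which 6.4 allows for by making diagnostic method by tone a secondary endpoint. If the error is an over-read in darker skin, it points the same way as the study hypothesis, and a larger sample would not reduce it.

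**Working it through.** The plan has no figure of its own for this point: it gives neither the TcB share of first readings nor a TcB bias by tone. The check is therefore a range under stated assumptions.

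**Inputs from the Protocol (10.1).** 20 hospitals × 28 infants = 560. Tone split 50/20/20/10%, hence 280, 112, 112 and 56 infants. Target differences from tone 1 of 10, 20 and 30 µmol/L. Simulated SD 10.

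**Assumed inputs.** TcB share p of 50% to 90%, equal across tones. Extra TcB over-read b in tone 4 relative to tone 1 of 10 to 30 µmol/L. SD 40 for the main illustration. On SD: a plain two-group calculation with SD 10 gives power near 100% for all three contrasts, not the stated 80%. An SD of about 32 returns about 80% for tone 2 versus 1. That mismatch is a separate matter, but it is why several SDs are shown.

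**1. Shift in the tone 4 versus 1 contrast = p × b**

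| TcB-first share | b = 10 | b = 20 | b = 30 |
|---|---|---|---|
| 50% | +5 | +10 | +15 |
| 70% | +7 | +14 | +21 |
| 90% | +9 | +18 | +27 |

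If instead the over-read is the same in every tone but the share differs, the shift is (p4 − p1) × b. With 90% in tone 4, 50% in tone 1 and b = 10, it is 0.4 × 10 = +4.

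**2. Chance of a significant tone 4 contrast with no true difference**

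SE = SD × √(1/280 + 1/56). At SD 40 this is 40 × 0.1464 = 5.86. The rejection rate is P(|Z| > 1.96) with Z centred at shift/SE.

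- SD 40, 70% TcB: shifts of 7, 14 and 21 give 22%, 67% and 95%.
- SD 32, 80% TcB, b = 5, 10 and 20: shifts of 4, 8 and 16 give 14%, 40% and 93%.
- SD 10 (the stated value), the same shifts: 78%, about 100% and 100%.

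A simulation of 20 hospitals × 28 (300 runs, hospital SD 10 assumed, hospital fitted as fixed, 80% TcB, extra bias 0/5/10/20 for tones 1 to 4) gave shifts of about 4, 8 and 16 for tones 2 to 4. At SD 32 it rejected in 18%, 54% and 89% of runs.

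**3. What separating the methods costs**

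In the same simulation, adding method and method-by-tone terms brought rejection back to about 3% to 7%. The tone coefficient then rests on SBR-first infants alone. At 70% TcB these number 0.3 × 280 = 84 in tone 1 and 0.3 × 56 = 16.8 in tone 4:

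- SE = 40 × √(1/84 + 1/16.8) = 10.7, which is 1.8 times 5.86.
- At 90% TcB (28 and 5.6 infants), SE = 40 × √(1/28 + 1/5.6) = 18.5, which is 3.2 times.

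**The case against.** The case against is substantial, and parts of it stand.

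- **Pooling is inferred.** The recruitment sentence is an alert to staff, not an outcome definition, and no sentence says TcB and SBR values are analysed together. This stands. The supportable statement is that the defining method is not given. A TcB-only outcome would not escape the problem: it would carry the full TcB error.
- **The covariate list is open.** The word confounders could include method, and an SAP not shown here may add it. This stands for covariate detail. It does not answer the endpoint wording or the interpretation, which the protocol itself fixes. A method main effect alone would also leave tone-dependent error in place.
- **A reader might infer that the protocol shows TcB over-reads in darker skin.** It does not. The sentence in 5.1 can be read as over-reading overall with only precision differing by group. That study had 201 mostly premature infants and no skin tone groups, and 5.1 also says ethnicity tracks neonatal skin tone poorly. Objective 2 shows that the question is open.
- **A reader might infer that Objective 1 cannot distinguish delay from artefact at all.** That goes too far. Age at first measurement and indication for testing are also primary endpoints in 6.3, and device error affects neither. They do not correct the absolute value, but the inference does not rest on it alone.
- **A reader might want the interaction model as the primary analysis.** The documents do not support this. Section 7 describes TcB as common after 24 hours and SBR as following TcB readings within a threshold of the treatment line. Section 9 adds no laboratory tests. SBR-first infants and TcB-SBR pairs are therefore selected, and pairs chosen on a high TcB invite regression to the mean. Method may also lie downstream of tone, and 10.2 warns against adjusting for mediators and colliders.

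**Conclusion.** The point holds in a limited form. The protocol does not say which method defines the Objective 1 outcome or how method enters its analysis, while treating TcB error as possibly dependent on skin tone. Followed as written, a tone difference in the first value could partly reflect device error.

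The size is unknown. The shift of +5 to +27 µmol/L in the tone 4 contrast rests on an assumed TcB share of 50% to 90% and an assumed extra over-read of 10 to 30 µmol/L. The top assumed bias equals the whole tone 4 target effect, so the upper end is a stress case. The rejection rates also depend on the SD chosen. The figures show that the artefact can be of the same order as the target effects, not that it will be. The documents do not support saying that a positive finding would be wholly artefact.

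**What to change.** In 6.3 and 10.2:

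1. State which method defines the Objective 1 outcome (first value by either method, or one named method), and align the reference to age at TcB measurement with it.
2. Keep the planned mixed model as primary. Pre-specify that tone contrasts are also reported separately for TcB-first and SBR-first infants.
3. Add a sensitivity analysis on an SBR-equivalent scale: SBR where it came first, otherwise TcB converted with the tone-specific differences from Objective 2, carrying their uncertainty into the interval.
4. State that a tone difference in TcB values alone is not evidence of later assessment unless it is consistent with items 2 and 3.
5. State the limits: SBR-first infants and TcB-SBR pairs are selected (by age under 24 hours and by TcB near the treatment line), and method may be downstream of tone. These are supporting analyses and do not replace the primary model.

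**Cost.** No new data are needed, since Table 1 already holds method, device and values. The price is precision: the SBR-first contrast for tone 4 has an SE of about 10.7 against 5.9 at 70% TcB-first and SD 40, and about 18.5 at 90%. The study is not sized for these analyses, so a non-significant SBR-first result should not be read as showing no difference.
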